5 STUDY POPULATION

5.1 NUMBER OF SUBJECTS

The study will consist of up to 30 centers in the United States each contributing about 10 subjects per center in order to obtain 300 evaluable subjects. We anticipate a 10% drop out rate during the trial for both Groups 1A and Group 2A, and 30% of subjects in Group 2A will switch to Group 2C and therefore a total of 225 subjects will be recruited. This trial employs an adaptive design therefore the enrollment numbers may be reduced or increased based on planned interim analysis.

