9.1.1 GENERAL

Descriptive statistical methods will be used to summarize the data from this study with hypothesis testing performed for primary and secondary endpoints. These include number of subjects (n), mean, median, standard deviation, minimum, and maximum for continuous data, and frequencies and percentages for categorical data. All data collected during the study will be reported and analyzed.

Unless specified otherwise, all statistical testing will be two-sided and performed using a significance (alpha) level of 0.05.

All statistical analyses will be conducted using PASW 19.

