from the mean change in wound area and protease activity between baseline and 4 weeks after 4 weeks of CelluTome™ + SOC (**Group 1A**) versus 4 weeks of SOC (**Group 2A**) will be equal for both groups. Formally, $H_0: r_1 - r_2 = 0$; $H_1: r_1 - r_2 = D_1 \neq 0$, where r_1 is the Pearson correlation coefficient for subjects in **Group 1A** calculated from difference in mean wound area and difference in mean protease activity between baseline and 4 weeks, r_2 is the same specified metric for subjects **Group 2A**, D_1 is the difference ($r_1 - r_2$) assuming the alternative hypothesis, and the statistical test used is Steiger's Z test with the assumption that r will have the same sign for both groups.

H5: Correlation of wound area with protease activity at 8 weeks

The Pearson correlation coefficient (or Spearman's rho in the case of severe non-normality) calculated from the mean change in wound area and protease activity between baseline and 8 weeks after 8 weeks of CelluTome™ + SOC (**Group 1A**) versus 8 weeks of SOC (**Group 2B**) will be equal for both groups. Formally, $H_0: r_1 - r_2 = 0$; $H_1: r_1 - r_2 = D_1 \neq 0$, where r_1 is the Pearson correlation coefficient for subjects in **Group 1A** calculated from difference in mean wound area and difference in mean protease activity between baseline and 8 weeks, r_2 is the same specified metric for subjects in **Group 2B**, D_1 is the difference ($r_1 - r_2$) assuming the alternative hypothesis, and the statistical test used is Steiger's Z test with the assumption that r will have the same sign for both groups.

H6: Reduction in pain score at 12 weeks

The change in mean pain score between baseline and at 12 weeks after 12 weeks of CelluTome™ + SOC (**Group 1A**) versus 12 weeks of SOC (**Group 2B**) will be equal for both groups. Formally, $H_0: \mu_1 - \mu_2 = 0$; $H_1: \mu_1 - \mu_2 = D_1 \neq 0$, where μ_1 is the mean difference in pain score for subjects in **Group 1A** between baseline and 12 weeks, μ_2 is the same specified metric in **Group 2B**, D_1 is the difference ($\mu_1 - \mu_2$) assuming the alternative hypothesis, and the statistical test used is the paired t test if data are normal and the Mann-Whitney test on a non-paired basis if data are non-normal.

H7: Proportion of wounds healed at 12 weeks (Groups 2B versus 2C)

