The first hypothesis to be tested is that the proportion of wounds healed in **Group 2C** (12 weeks of SOC + 2 CelluTome™ applications) is no more than 15% lower than the proportion of wound healed in **Group 2B** (12 weeks of SOC). Noninferiority is established if the lower limit of the $(1 - 2\alpha) \times 100\%$ CI (confidence interval) for the difference (**Group 2C** – **Group 2B**) is above -15% where the equivalence margin, δ , is 15%. If non-inferiority is not established because the proportion of wounds healed in **Group 2C** is much higher than in **Group 2B**, the superiority hypothesis testing used in H2 will be utilized.

H8: Incidence of Adverse Events (AEs) (Groups 2B versus 2C)

The incidence of adverse events (AEs) by 12 weeks after 12 weeks of CelluTome™ + SOC (**Group 2C**; maximum of 2 CelluTome™ applications) versus 12 weeks of SOC (**Group 2B**) will be equal for both groups. Formally, $H_0: I_1 - I_2 = 0$; $H_A: I_1 - I_2 = D_1 \neq 0$, where I_1 is the incidence of AEs for **Group 2C** on a per subject basis, I_2 is same metric for **Group 2B**, D_1 is the difference ($I_1 - I_2$) assuming the alternative hypothesis, and statistical test used is the Mann-Whitney test.

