- Proportion of wounds healed at 12 weeks will be analyzed by chi square (unadjusted); this endpoint may also be analyzed using logistic regression to adjust for the following variables (with and without covariate imputation) if needed:
 - Site
 - Year enrolled (if trial lasts 2 years or more)
 - Treatment group
 - Initial area at randomization (cm²)
 - Initial wound depth (cm)
 - Age of wound at enrollment (days)
 - Smoking status
 - Prior VLU
 - Pain score at randomization

- Patient age
- Gender
- Ethnicity/race
- VCS score
- Diabetes
- Patient on pain medications
- Smoking status
- BMI
- Infection episodes

Note: unadjusted testing for **Group 2C** versus **2B** will be non-inferiority, followed by superiority testing if the former fails and proportion of wounds healed in **Group 2C** is much higher than in **Group 2B**.

- A summary of the incidence of adverse events (count by patient):
 - AE (category)
 - SAE (category; brief description; resolution; should include death)
 - When event happened in relation to start of treatment (days)
 - Associated patient ID, site ID

Incidence of AEs will be analyzed by Mann-Whitney test on a per subject basis.

- Correlation of changes in wound area with changes in protease activity will be first analyzed by calculating the Pearson correlation coefficient for each group or Spearman's rho if data are grossly non-normal. For each subject the change in protease activity is calculated by subtraction of the value at 4 or 8 weeks from the value at baseline; reduction in wound area is calculated similarly. Differences in r will be analyzed using Steiger's Z test with the assumption that r will have the same sign for both groups. If significant differences are found between groups, further analysis using GLM doubly multivariate repeated measures (change in wound area and protease activity between baseline and 4 and 8 weeks) to adjust for the following variables (with and without covariate imputation) may be undertaken (ordinal re-categorization will be done if data are severely non-normal):
 - Site
 - Year enrolled (if trial lasts 2 years or more)
 - Treatment group
 - Initial area at randomization (cm²)
 - Initial wound depth (cm)
 - Age of wound at enrollment (days)
 - Smoking status
 - Prior VLU
 - Pain score at randomization
 - Patient age
 - Gender
 - Ethnicity/race
 - VCS score

CELLUTOME™ IN VENOUS LEG

- Diabetes
 - Patient on pain medications
 - Smoking status
 - BMI
 - Infection episodes

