- Reduction in pain score (baseline – Week 12) will be analyzed by paired t test if the dependent variable data are not grossly non-normal or the Mann-Whitney test if they are grossly non-normal (unadjusted).

To create the flow chart, the following numbers will be required for each group: eligible (n), screened (n), screen failure (n, with categorical reasons), randomized (n), completed 12 weeks study (n), withdrawals or lost to follow-up after randomization (n, with categorical reasons).

These variables are required for the final analysis:

- Site ID (alphanumeric)
- Patient ID (alphanumeric)
- Year enrolled (numeric; date, year only)
- Group assignment (nominal factor, [1A, 2A, 2B, 2C]; note: subjects in 2A can also have 2B or 2C assignments as well)
- Lost to follow up (binomial factor [1,0; 1 = yes]; estimated date lost to follow-up; associated patient ID; categorical reason for lost to follow-up)
- Death during study (binomial factor [1,0; 1 = yes]; estimated date when death occurred)
- Gender (nominal factor [1, 0; male = 1])
- Subject age at S1 (continuous variable with breakpoint at > 90 years if > 90)
- Ethnicity/race (multinomial factor)
- Smoking status at S1 (ordinal factor: [1, 2, 3; never, ever, current])
- Wound count (Poisson distribution variable; count of VLU at patient level at randomization)
- Index Ulcer location (multinomial factor)
- Prior VLU at S1 (binomial factor [1,0; 1 = yes])
- Wound age at S1 (continuous variable, days; S1)
- Pain score (continuous variable, 0-10, TV1 and 13)
- VCS score at S1 (continuous variable, 0-24)
- BMI at S1 (continuous variable)
- Diabetes at S1 (nominal factor [1, 0; yes = 1])
- Subject on pain medication at S1 (nominal factor [1, 0; yes = 1])
- Wound area (continuous variable, cm²; weekly, weeks TV1-13)
- Wound depth (continuous variable, cm; weekly, weeks TV1-13)
- Outcome healed at 12 weeks (binomial factor, [1,0; 1 = yes])
- Time to heal (continuous variable, 0-84, days after randomization for healed wounds)
- Initial wound healed within 12 weeks and confirmed closed about 2 weeks later (binomial, [1,0; 1 = yes])
- Ulcer recurrence by 12 weeks (binomial factor, [1,0; 1 = yes]; estimated days after randomization when event occurred)
- Infection episode (Poisson variable, weeks TV1-13)
- AE (Poisson distribution variable, count at patient level; date of onset)

CELLUTOME™ IN VENOUS LEG

- TEAE (Poisson distribution variable, count at patient level for each of 4 categories; date of onset)

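### SAP 9.2 and 9.7, secondary tests: H6 names a paired t test for two separate groups, and H7 opens superiority only after a failure that a higher 2C rate cannot cause; minor: Steiger's Z in H4/H5

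*Combined protocol and SAP*

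**What the plan says.** **H6, pain.** SAP 9.2 sets a between-group null, mu1 - mu2 = 0, for mean change in pain from baseline to week 12 in Group 1A versus Group 2B. For the test it says: "the statistical test used is the paired t test if data are normal and the Mann-Whitney test on a non-paired basis" otherwise. In 9.7 the same endpoint "will be analyzed by paired t test if the dependent variable data are not grossly non-normal", with Mann-Whitney as the alternative.

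**H7, healing in 2C versus 2B.** In 9.2: "Noninferiority is established if the lower limit of the" (1 - 2 alpha) interval for the 2C minus 2B difference "is above -15% where the equivalence margin" is 15%. The route to superiority follows: "If non-inferiority is not established because the proportion of wounds healed in Group 2C is much higher than in Group 2B", the chi-square test of H2 is used. In 9.7 the order is non-inferiority, "followed by superiority testing if the former fails and proportion of wounds healed in" Group 2C is much higher. Neither section defines much higher.

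**H4 and H5.** Sections 9.2 and 9.7 compare the area-protease correlation in 1A with that in 2A (week 4) or 2B (week 8) by Steiger's Z.

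**General.** Section 9.1.1: "all statistical testing will be two-sided and performed using a significance (alpha) level of 0.05".

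**The concern.** Each of these pre-specified tests fails to match its own hypothesis.

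- **H6.** The normal-data branch cannot be carried out for the stated null. If an analyst makes it computable by running it within each arm, it answers another question: whether pain changed from baseline.
- **H7.** The plan intends a superiority test when 2C does much better, but makes it conditional on an event that a better 2C result works against.
- **H4/H5.** The named test is built for correlations measured in the same subjects, and these groups share none.

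At stake is pre-specification: in each case someone must choose a different procedure, possibly after seeing the data. All are secondary analyses.

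**Working it through.** **Plan's own figure.** The only power figure is 86.1% for the primary log-rank test (9.3). It reproduces: 85.7% by a Lakatos-type calculation with 113 versus 112 subjects, 50% control healing, hazard ratio 1.74 and the stated weekly dropout. It does not bear on H4 to H7, for which no power is stated.

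**Group sizes.** Section 9.3 gives 113 control and 112 treatment subjects. Section 5.1 expects that "30% of subjects in Group 2A will switch to Group 2C".
- 2C = 113 x 0.30 = 34; 2B = 113 - 34 = 79.
- After the 10% dropout in 5.1: 34 x 0.9 = 31 and 79 x 0.9 = 71.

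**H6.** There are about 112 subjects in 1A and 79 in 2B, with no matching, so no paired differences exist across groups. Within one arm, the paired statistic is t = m / (SD / sqrt(n)), where m is that arm's mean change; mu1 - mu2 does not enter it. To illustrate (m and SD are assumed), take an equal mean fall of 1 point in both arms with SD 3.5:
- 1A: 1 / (3.5 / sqrt(112)) = 3.02, p = 0.003
- 2B: 1 / (3.5 / sqrt(79)) = 2.54, p = 0.013

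Both are significant although the arms do not differ. In simulation with equal true falls of 1 or 2 points and SD 2 to 3 (assumed), the within-arm test rejected in 84% to 100% of trials per arm. A Welch two-sample test rejected in 4.6% to 6.0%.

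**H7.** With alpha 0.05 the (1 - 2 alpha) interval is 90%. H7 does not restate alpha, so 95% is shown too.

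The largest possible 90% Wald half-width at 34 versus 79 is 1.645 x sqrt(0.25/34 + 0.25/79) = 0.169. The lower limit can therefore be at or below -0.15 only if the observed 2C lead is at most 0.169 - 0.150 = 0.019. Enumerating every 2x2 table, with uncorrected chi-square at two-sided 0.05, gives:

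| 2C / 2B | Interval | Largest 2C lead still failing | Tables failing non-inferiority with 2C significantly higher |
|---|---|---|---|
| 34 / 79 | 90% | 1.5 points | 0 |
| 34 / 79 | 95% | 4.8 points | 0 |
| 31 / 71 | 90% | 2.3 points | 0 |
| 31 / 71 | 95% | 5.7 points | 0 |

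At 34 versus 79, 979 of 2,800 tables have 2C significantly higher, and none fails non-inferiority. Failures with 2C slightly ahead come from a wide interval, not from a high 2C rate.

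Example: 24/34 versus 40/79. Difference 0.200, SE 0.0963, 90% interval +4.1 to +35.8 points, p = 0.0496 (0.079 with continuity correction). Non-inferiority is met, so the written rule does not reach superiority. Under a two-sided equivalence rule with limits of -15% and +15%, the same result fails through the upper limit, and the wording would then make sense.

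**How likely is a large 2C lead?** 2C is the controls with less than 40% area reduction at TV7.
- With 50% control healing overall (9.3) and 30% in 2C, assume the 2C subjects would have healed at 0% to 30% on standard care. Then 2B heals at 0.5/0.7 = 71% down to (0.5 - 0.3 x 0.3)/0.7 = 59%.
- Applying the hazard ratio of 1.74 to 2C for the remaining six weeks (exponential healing, none healed at TV7; assumed) gives 1 - 0.5^(1.74 x 6/12) = 1 - 0.5^0.87 = 45%.
- With 2C at a more generous 50% and 2B at 60% to 70%, the binomial probability of a significant result favouring 2C is at most about 0.2%.

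**H4/H5.** The independent-samples Fisher standard error is sqrt(1/(n1-3) + 1/(n2-3)). Steiger's form with zero covariance and one common n reduces to sqrt(2/(n-3)); this is one possible implementation.
- H4, 112/113: 0.1351, against 0.1355 or 0.1348; off by 0.2%.
- H5, 112/79: 0.1494, against 0.1355 (n = 112, 9.4% too small) or 0.1622 (n = 79, 8.6% too large).

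**The case against.** **H6 corrects itself.** The null, the group definitions and the non-paired wording of the Mann-Whitney branch all show that an unpaired comparison was meant, and a paired procedure would stop at programming with unequal groups. This stands as to intent. A reader might infer that the sponsor plans within-arm tests; the documents never propose them, and the illustration shows only what that workaround would do. The text is still wrong in two sections.

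**H7 may have meant equivalence.** The phrase equivalence margin points that way. But the decision rule uses only the lower limit, so the text has to say which was meant.

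**H7 rarely matters.** This stands. A reader might infer that the gate would block many true superiority findings. If 2C were truly 20 to 25 points above 2B, a significant chi-square would indeed be common. The plan's inputs do not support that scenario: 2C is selected for poor response and has six weeks left. Setting 2B at 30%, for instance, would require the 2C subjects to heal at (0.5 - 0.7 x 0.3)/0.3 = 97% on standard care to keep control healing at 50%.

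**The test name is not the main obstacle.** This also stands. 2B and 2C are defined by response after randomization, so correcting the tests does not make 1A versus 2B or 2C versus 2B a randomized comparison.

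**H4/H5 is small and depends on implementation.** Agreed; it is graded minor.

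**Conclusion.** Wrong as written, for secondary analyses only.

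- **H6:** the named parametric test cannot address the stated between-group null. This needs no numerical assumption.
- **H7:** the gate is incoherent. Across both sets of sizes and both interval levels, non-inferiority fails only when 2C leads by at most 1.5 to 5.7 points, and never together with a significant chi-square in favour of 2C. This rests on Wald intervals and the 30% switch rate in 5.1. The gain from repair is a coherent rule, not a large change in expected results.
- **H4/H5:** negligible at 112/113, and under 10% of the standard error at 112/79.

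The primary log-rank test is untouched. The corrected H6 and H7 must still be read as non-randomized comparisons.

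**What to change.** - **H6 (9.2 and 9.7):** replace the paired t test with an independent-samples Welch t test on change in pain; keep the unpaired Mann-Whitney alternative.
- **H7 (9.2 and 9.7):** state that superiority is tested once non-inferiority is met (lower limit above -15%). If two-sided equivalence was meant, say so and give both limits, -15% and +15%. State the interval level, and how the superiority p-value enters the Hochberg procedure in 9.7.
- **H6 and H7:** add a sentence that 2B and 2C are formed by response at TV7, so these comparisons are not protected by randomization.
- **H4/H5 (9.2 and 9.7):** replace Steiger's Z with the Fisher r-to-z test for independent samples, SE = sqrt(1/(n1-3) + 1/(n2-3)), with a suitable variance or a bootstrap interval if Spearman's rho is used.

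Cost: SAP wording only. No new data and no change to the sample size.

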	
CelluTome™ system at TV1, TV5 and TV9, visits plus SOC (multi-layer compression) (Group 1A) (2) SOC alone (Group 2A).
 
At TV 7, wound assessment will be carried out to evaluate wound healing in Group 2A. Subjects in Group 2A, whose percentage area reduction (PAR) is <40% will be allowed to have CelluTome™ treatment in addition to continuation of SOC and will constitute Group 2C. Group 2C subjects will receive a graft at TV7 and TV11. The remainder of Group 2A subjects will be termed Group 2B subjects. Patient codes will still remain the same to enable tracking continuity.
 
During the Treatment Phase, the wound will be swabbed for protease activity for Group 1A and 2A/B subjects: TV1 (In Group 1A this will be prior to CelluTome™ application), TV5 and TV9 visits.
 
Subjects will be evaluated on a weekly basis during the Treatment Phase. Effectiveness evaluations each week will include Investigator assessment of wound healing and measurements of ulcer size using digital planimetry. At TV4 and TV8, Prisma™ is to be applied to the study ulcer for Group 1A, 2A, and 2B subjects. Group 2C subjects will receive Prisma™ at TV10. Safety evaluations during the Treatment Phase will consist of adverse event assessments at each visit.

Dosage and Frequency of Administration
	
Epidermal grafting will be applied up to three times in Group 1A: TV1, TV5 and TV9. Group 2C subjects will receive up to two grafts: TV7 and TV11.

Duration of Study
	
A run-in period of 2 weeks followed by 12 weeks of active treatment.

Statistical Methods, Power, and Sample Size Calculations
	
Please see the Statistical Analysis Plan in the protocol.

Protease Levels
	
Absolute values of inflammatory proteases (Neutrophil elastase, MMP 8 and 9) will be measured at S1 before application of Prisma™, day 0 before application of Epidermal grafts and week 4 and 8 visits thereafter to determine the effect of protease levels on graft success for Group 1A and 2A/B subjects. The results will be blinded to the Investigators.

Key Words
	
Epidermal Grafts Chronic Wounds Clinical Trial Venous Leg ulcer Protease levels in chronic wounds

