The Treatment Phase (TV1 to TV13) Begins with a series of assessments designed to confirm the subjects’ continued eligibility. Investigators will debride the ulcer. Subjects whose ulcers continue to meet eligibility criteria will then be randomized to one of two groups: (1) One application of epidermal microdome at day zero and standard of care (**Group 1A**) OR (2) standard of care: multi-layer compression (**Group 2A**) (see figure on next page).

During the Treatment Phase, subjects will be evaluated on a weekly basis. Effectiveness evaluations each week will include Investigator assessment of wound healing and measurements of ulcer size using digital photos.

At TV 7, wound assessment will be carried out to evaluate wound healing in **Group 2A**. Subjects in **Group 2A**, whose percentage area reduction (PAR) is <40% will be allowed to have CelluTome™ treatment in addition to continuation of SOC and will constitute **Group 2C**. **Group 2C** will receive a graft at TV7 and TV11. The remainder of **Group 2A** subjects will be termed **Group 2B** subjects. Patient codes will still remain the same to enable tracking continuity.

[figure not shown]
During the Treatment Phase, the wound will be swabbed for protease activity for **Group 1A and 2A/B** subjects: TV1 (In **Group 1A** this will be prior to CelluTome™ application), TV5 and TV9 visits.

Subjects will be evaluated on a weekly basis during the Treatment Phase. Effectiveness evaluations each week will include Investigator assessment of wound healing and measurements of ulcer size using digital planimetry. At TV4 and TV8, Prisma™ is to be applied to the study ulcer for **Groups 1A, 2A, and 2B** subjects. **Group 2C** subjects will receive Prisma™ at TV10. Safety evaluations during the Treatment

CELLUTOME™ IN VENOUS LEG

Phase will consist of adverse event assessments at each visit.

Diagram showing progress of trial and the different subjects groups. Up to 6 weeks from randomization only **Groups 1A and 2A** exist; after 6 weeks, **Groups 1A, 2B, and 2C** exist.

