6.1 VISIT WINDOWS

Subject visit dates must be scheduled within the visit windows detailed on the Schedule of Events tables. One week equals 7 days.

During the Screening Phase, each visit is scheduled from the S1 visit date, with reference to the allowed visit window.

During the Treatment Phase, each visit is scheduled from the TV1 visit date, with reference to the allowed visit window. For example, the TV2 visit is scheduled for 1 week \pm 2 days after the TV1 visit. TV3 is scheduled for 2 weeks \pm 2 days after the TV1 visit.

SCHEDULE OF EVENTS

Visit	SVs (14 days)	TV1 (rand)	T V	TV3	TV4	TV5	TV6	TV7	TV8	TV9	TV10	TV11	TV12- 13
Weeks from Randomization Date			+1	+2	+3	+4	+5	+6	+7	+8	+9	+10	+11-12
Window Period	0		±2 da	±2 days	±2 days	±2 days	±2 days	±2 day	±2 days	±2 days	±2 days	±2 days	±2 days
Assessment of eligibility	√												
Medical history	√												
Apply Prisma™	√				√				√		√ ^[B]		
Randomization		√											
Ulcer assessments	√		√	√	√	√	√	√	√	√	√	√	√
Physical exam	√												
Vital signs	√												
Pain assessment	√		√	√	√	√	√	√	√	√	√	√	√
Study ulcer photographs	√		√	√	√	√	√	√	√	√	√	√	√
Study ulcer cleaning	√		√	√	√	√	√	√	√	√	√	√	√
Study ulcer debridement	√ ^[A]		√	√	√	√	√	√	√	√	√	√	√
Study ulcer swab	√	√				√				√			
Assessment of compression bandaging	√		√	√	√	√	√	√	√	√	√	√	√
Epidermal graft application		√				√		√ ^[B]		√		√ ^[B]	
Study ulcer dressings and compression therapy	√	√	√	√	√	√	√	√	√	√	√	√	√
Study ulcer closure assessment			√	√	√	√	√	√ ^[C]	√	√	√	√	√
Assess for concomitant medications	√	√	√	√	√	√	√	√	√	√	√	√	√
Assess for AEs and SAEs		√	√	√	√	√	√	√	√	√	√	√	√
Quality of Life, PBI-P and Time-trade off questionnaires		√				√				√			√ ^[D]

[A] – If required per the Investigator’s judgment.

[B] – **Group 2C** subjects only

[C] – Evaluation of wound area reduction since TV1. Subjects in **Group 2A** (SOC), whose study ulcer PAR is < 40%, will become **Group 2C**; the remainder of **Group 2A** subjects will become **Group 2B**

[D]- Questionnaires are to be completed for TV13 only

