8.4.2 MEDICAL HISTORY

A medical history will be recorded during the Screening Period and will include:

- ALL ongoing medical conditions
- ALL previously resolved medical conditions related to Venous Insufficiency or Leg Ulceration or which are relevant in the opinion of the Investigator
- ANY prior medical conditions that have resolved within the last year

Events that emerge prior to the randomization visit (TV1) will be recorded in the medical history and not as Adverse Events. Aside from being used to determine subject eligibility, this information will permit the Investigator to record the nature, duration and severity of any ongoing baseline medical conditions prior to receiving investigational product treatment.

Medical histories will be recorded using the body system categories outlined below:

- Cardiovascular
- Respiratory
- Gastrointestinal
- Renal
- Hepatic
- Lymphatic
- Hematologic
- Immunologic
- Dermatologic
- Psychiatric

CELLUTOME™ IN VENOUS LEG

- Neurological
- Endocrine
- Genitourinary
- Other

For each relevant history, the following will be documented:

- Disease/disorder/condition
- Date of diagnosis
- History status (resolved or ongoing)

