9.1 BRIEF TRIAL DESCRIPTION

THIS TRIAL IS A RANDOMIZED CONTROLLED TRIAL (RCT) IN WHICH SUBJECTS WITH VENOUS LEG ULCERS (VLUS) WILL BE RANDOMIZED 1:1 TO A MAXIMUM OF 3 TREATMENTS OF CELLUTOME™ 4 WEEKS (GROUP 1A) OR STANDARD OF CARE (SOC; GROUP 2A) AND FOLLOWED FOR 12 WEEKS. PRIMARY ENDPOINT IS TIME TO HEAL WITHIN 6 AND 12 WEEKS. IF WOUNDS IN GROUP 2A HAVE NOT BEEN REDUCED IN AREA BY AT LEAST 40% BY 6 WEEKS, PATIENTS WILL BE ALLOWED TO RECEIVE CELLUTOME™ TREATMENT (GROUP 2C; 2 TREATMENTS WITHIN THE REMAINING 6 WEEKS). THE REMAINDER OF THE SOC PATIENTS WILL BECOME GROUP 2B.

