10.1 ADVERSE EVENTS

An adverse event (AE) is defined as any unfavorable or unintended sign, symptom, or disease that occurs or is reported by the patient to have occurred, or a worsening of a pre-existing condition. An adverse event may or may not be related to the treatment regimen. All AEs and intercurrent illnesses must be recorded in the subject's medical records and on the CRF.

Adverse events will be defined as those events that occur after signing the informed consent until the final study visit. A description of the AE along with the onset date, end date, severity, action taken, treatment, outcome, likely cause, and relationship to the study products will be recorded in the CRF.

Local and systemic AEs associated with each treatment arm will be tabulated and compared. AEs will be elicited through direct questioning, subject reports, and physical examination.

An abnormal laboratory test result is not by itself considered to be an AE unless the Investigator considers the finding of clinical significance that should be reported in such a manner.

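### H8 describes Group 2C as having 12 weeks of CelluTome, but its first graft is at week 6, so about half of the adverse-event window in the 2C versus 2B test predates CelluTome

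*Combined protocol and SAP*

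**What the plan says.** H8 (Section 9.2) tests AE incidence in Group 2C against Group 2B. It describes the 2C side as "The incidence of adverse events (AEs) by 12 weeks after 12 weeks of CelluTome™ + SOC", with a cap of two applications, and the 2B side as 12 weeks of SOC. The test is Mann-Whitney on a per-subject basis, and Section 9.7 repeats this.

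The rest of the document places CelluTome in Group 2C later:

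- Synopsis, dosage row: "Group 2C subjects will receive up to two grafts: TV7 and TV11".
- Section 9.1, on Group 2C: "2 TREATMENTS WITHIN THE REMAINING 6 WEEKS".
- Section 4: "At TV 7, wound assessment will be carried out to evaluate wound healing in" Group 2A. Those with an area reduction below 40% become 2C and the remainder become 2B. Up to week 6 only Groups 1A and 2A exist.
- Section 6.1, Schedule of Events: TV7 is week +6, TV11 is week +10 and the last visit, TV13, is week +12, each with a window of 2 days either side.
- H7, immediately before H8, describes 2C as 12 weeks of SOC plus two CelluTome applications, which fits the schedule.

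The start of AE counting is stated in two ways. Section 8.4.2: "Events that emerge prior to the randomization visit (TV1) will be recorded in the medical history and not as Adverse Events". Section 10.1: "Adverse events will be defined as those events that occur after signing the informed consent until the final study visit".

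**The concern.** An AE in weeks 0 to 6 of a 2C subject cannot have been caused by a graft that had not yet been placed. H8 nevertheless counts it on the CelluTome side of the comparison. The ungrafted weeks dilute any graft-related effect in relative terms and add background events to a test in a group expected to have only about 34 subjects.

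The groups may also be observed for different lengths of time. Every 2C subject is, by definition, on study with an open ulcer at TV7. Group 2B is the remainder of 2A, so it includes ulcers that closed earlier, and Section 6.4 treats a subject with a closed ulcer as having completed the study. The per-subject count makes no allowance for time on study.

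Early events can also influence group membership. Section 8.7.2 requires every study-ulcer infection to be recorded as an AE and lists increased surface area among its signs. An infection before TV7 can therefore enter the AE count and also help to put the subject in 2C.

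**Working it through.** **Exposure.** A treatment visit TVk falls k − 1 weeks after TV1, and treatment runs to week 12 (Synopsis: "A run-in period of 2 weeks followed by 12 weeks of active treatment").

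- Group 1A (H3, same phrase): first graft at TV1 = week 0, so 12 − 0 = 12 weeks. The stated duration reproduces.
- Group 2C (H8): first graft at TV7 = week 6, so at most 12 − 6 = 6 weeks. The stated 12 weeks does not reproduce.

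**Share of the AE window before the first graft in 2C.**

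- Nominal, counting from TV1: 6/12 = 50%.
- Visit windows of ±2 days at TV7 (day 42) and TV13 (day 84): from 40/86 = 46.5% to 44/82 = 53.7%.
- Counting from consent instead (Section 10.1): (2 + 6)/(2 + 12) = 57% if consent is at S1 with a 14-day screening phase, or (4 + 6)/(4 + 12) = 62.5% if consent is 14 days before S1.
- A 2C subject who stops observation between TV7 and week 12 has a larger pre-graft share.

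**Dilution.** Assume a constant weekly AE rate before the graft, multiplied by r afterwards, and full follow-up. The 12-week mean count, relative to no graft effect, is (6 + 6r)/12.

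| True post-graft rate ratio r | Apparent 12-week ratio |
|---|---|
| 1.5 | 1.25 |
| 2 | 1.5 |
| 3 | 2.0 |

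The absolute excess of events is unchanged; it is set against twice the background time. Mann-Whitney compares ranks rather than means, so the table is an illustration.

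**Group 2B subjects healed before TV7.** Inputs: 113 controls and 50% healed (Section 9.3), taken as the 12-week proportion; 30% of 2A switching to 2C (Section 5.1). Expected 2C = 0.3 × 113 = 34; expected 2B = 0.7 × 113 = 79, held fixed below. The constant hazard is −ln(0.5)/12 = 0.0578 per week.

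| Assumed healing pattern | Healed by week 6 | Share of 79 |
|---|---|---|
| Constant hazard, no dropout: 113 × (1 − exp(−0.0578 × 6)) | 33.1 | 42% |
| Constant hazard, dropout 0.0083 per week | 32.3 | 41% |
| Constant hazard, dropout 0.033 per week | 30.2 | 38% |
| Weibull shape 1.5, no dropout: 113 × (1 − 0.5^(0.5^1.5)) | 24.6 | 31% |
| Weibull shape 2, no dropout: 113 × (1 − 0.5^(0.5^2)) | 18.0 | 23% |

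The Weibull shapes are illustrative, and all rows without dropout keep 50% healed at week 12. The 23% to 42% is the spread of these cases, not a bound.

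**The case against.** The best defence is that H8 contains a copying slip. Its phrase is the H3 sentence for Group 1A, where 12 weeks is correct. H8's own parenthesis caps 2C at two applications, H7 describes 2C correctly, and every scheduling section agrees on TV7 and TV11. No one would be given the wrong treatment. Section 9.7 also asks for the timing of each event relative to start of treatment and collects onset dates and a treatment-emergent count. Section 10.4 requires a causality rating for each AE, so graft-related events can be separated in the listings. H8 is one secondary comparison of non-randomised groups, and the primary endpoint is untouched.

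Most of this stands, and it limits the weight of the point. It does not remove it. The listings leave the H8 test as it is, start of treatment is not defined for 2C, and correcting the phrase alone would leave weeks 0 to 6 in the count.

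A reader might infer more than the documents support:

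- *That half the window predates treatment.* It predates CelluTome; SOC runs throughout.
- *That about 42% of 2B would have healed by week 6.* That needs a constant hazard and no dropout. Section 9.3 gives a proportion healed, not a hazard shape.
- *That healed 2B subjects have definitely left before week 6.* Section 6.4 counts them as completed, but Section 6.3 schedules a healing confirmation visit, Section 9.6 requires closure to be confirmed two weeks later, and Section 9.7 collects recurrence by 12 weeks. AE follow-up after healing is unclear and may be shorter; more cannot be said.
- *That the bias has a known direction.* Dilution pulls a graft effect towards no difference, while shorter observation in 2B would raise 2C counts relative to 2B. The net direction is unknown.

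**Conclusion.** The point holds. H8 states a CelluTome exposure for Group 2C that the schedule contradicts: at most 6 weeks, not 12. The planned test counts AEs over the full period, nominally 50% of it before any graft (46.5% to 53.7% across the visit windows, more if counting starts at consent). This part rests only on visit arithmetic and does not depend on how quickly ulcers heal.

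The size of the dilution (a doubling seen as 1.5-fold) assumes a constant pre-graft AE rate and full follow-up. The imbalance in observation time is a possibility rather than an established fact. The roughly 23% to 42% of 2B healed before TV7 assumes 50% control healing at week 12 and 30% switching, and varies with hazard shape and dropout.

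Run as written, H8 would give a diluted and partly misattributed safety comparison. It should be corrected, but the consequence is confined to this secondary analysis.

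**What to change.** Amend H8 and the matching AE text in Section 9.7:

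1. Describe Group 2C as H7 does (12 weeks of SOC plus two CelluTome applications), keeping H8's existing statement that two is the maximum.
2. Count only AEs with onset from TV7 onward, in both groups, and define start of treatment for 2C accordingly.
3. Compare 2C with the 2B subjects still on study and unhealed at TV7, as AE rates per week on study. Report weeks 0 to 6 separately.
4. Label the comparison descriptive. State that 2B and 2C are non-randomised groups selected on area reduction at TV7. Restricting 2B to unhealed subjects and using rates addresses observation time, but confounding by healing speed remains.
5. State how long AEs are followed after an ulcer heals, and reconcile Sections 8.4.2 and 10.1 on when AE counting starts.

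The AE analysis changes need SAP wording only, because AE onset dates are already among the required variables in Section 9.7. Item 5 clarifies protocol text. The downside is fewer events and a smaller comparator group, so the estimates will be less precise.
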